1. Counseling twice weekly on diet and nutrition will improve food choices to more healthy choices of fresh fruits and vegetables and low fat protein sources. To test this hypothesis, patients will undergo a food frequency questionnaire at baseline to document choices prior to intervention. A food frequency questionnaire will be performed at the end of the intervention to determine the effect of counseling on protein source, number of calories, and frequency of fresh fruits and vegetables. Counseling will consist of the diabetes prevention program counseling which is a well-established, well-verified intervention, commonly accepted as an effective means of providing a standardized nutritional education.

2. The combination of exercise and dietary intervention positively affects body composition. With this hypothesis we will test whether muscle strength (Biodex measurements) and muscle mass (DEXA scan) changes after 12 months of an exercise intervention. We hypothesize that the transplant itself will not affect activity levels, strength levels or muscle mass. Baseline measurement will be performed before the intervention, at 6 months post intervention, and the final measurement would be taken at 12 months with muscle mass measured by DEXA and strength measured again by Biodex.

3. Patients receiving strength training will have significantly higher activity levels when compared with no intervention or physical therapy. The rationale for this hypothesis is that patients without strength training will fail to increase muscle mass and strength and this inability will translate to persistently lower activity levels than those patients with strength training. Once again levels will be documented with an accelerometer and PROMIS questionnaires, 6 months and 12months to document the effect of intervention. In addition, if patients in the control group and GH group decide to

have the optional muscle biopsy, it will help evaluate how targeted exercise may change muscle development measuring expression of mature microRNAs using total RNA extraction.

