4. Patients with strength training will activate type II macrophages which are anti-inflammatory and pro-regenerative, tipping the balance away from inflammation towards regeneration when compared to the other treatment groups. Since strength training is likely to initiate signals of muscle regeneration, and since type II macrophages play a key role in this effect, it is possible that increasing the signaling to the muscle for regeneration may also increase the proportion of active type II macrophages which are anti-inflammatory. To test this hypothesis, we will test the proportion of peripheral blood M1/M2 macrophages at baseline, 6 months and 12 months after the initiation of the intervention. Recognizing that immunosuppression may significantly confound this proportion and overall suppress it, we will also test circulating levels of pro-inflammatory cytokines such as C-reactive protein(CRP), IL-6, IL-1, TNF-alpha, homocysteine, adiponectin, leptin, and resistin as well as pro-regenerative cytokines such as TGF-beta and IL-10.

5. We expect patients with strength training will experience less renal dysfunction, decreased hemoglobin A1C, increased peripheral vascular function, decreased fasting blood sugar when compared to the other treatment groups. The rationale for this hypothesis is the finding that muscle mass provides active regulation of glucose and other metabolites. Therefore increasing this may provide improved metabolic function. These laboratory panels are part of the standard transplant follow-up labs and add no cost to the project.

6. Patients with strength training will have an overall improved sense of well-being and energy level compared to those with physical therapy or no treatment. With twice weekly counseling for activity and nutrition, patients will be asked about their general health, mental health and pain intensity using the PROMIS questionnaires.

METHODS

Setting: The study will include 225 patients, to achieve a goal of 180 patients in the GH study group and 45 patients in the control group. Every patient will be followed for 3 years after the start of the intervention. Patients will start the intervention at least 2 months post-transplant; however they can be enrolled prior to transplant.

Main Study Inclusion criteria:

- Successful kidney transplantation (KTx) with primary graft function
- Age between 18 and 65 years

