- Control group: patient will be treated according to the standard of care for post-transplant recipients; control patients will be offered the opportunity to undergo the GH regimen for the 1 year after their final visit as a control patient. If the control patients chose to undergo the GH regimen, the extended follow up will be completed after 1 year from their final GH visit (totaling 4 years from the start of intervention).

Long-term follow-up

After the 12 month intervention period all patients will be followed for 2 additional years. Patients will be contacted by phone to assess current activity level, employment status, graft function and current weight. Patient's medical records will also be reviewed to confirm BMI and graft function. This will be done every 6 months.

A separate waiver of documentation of consent, for long-term follow up, is being requested for patients that have previously enrolled and completed the study (January 3, 2012 to July 28, 2014).

Parameters to analyze in all patients:

The PROMIS v.1.1 - Global Health short form will be administered to all patients at the time of enrollment, 6 months and at the end of the study (12 months). The PROMIS v.1.1 - Global Health short form will assesses health in general (i.e. overall health). The PROMIS Global Health short form is a 10-item instrument representing multiple domains (physical function, fatigue, pain, emotional distress, social health) as well as perceptions of general health that cut across domains. Global items allow respondents to weigh together different aspects of health to arrive at a “bottom-line” indicator of their health. Similar global health items have been found predictive of future health care utilization and mortality.

PROMIS 29 Profile v2.0 will be administered to all patients at the time of enrollment, 6 months and at the end of the study (12 months). The PROMIS 29 Prolife v2.0 is a short form containing four items from seven PROMIS domains (Depression, Anxiety, Physical Function, Pain Interference, Fatigue, Sleep Disturbance, and Ability to Participate in Social Roles and Activities) along with a single item on Pain Intensity.

Multiple studies have been conducted by the PROMIS Network validating these instruments. Studies are shown at: <http://www.nihpromis.org/science/validitystudies.aspx>

Body composition and strength

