In the upper extremities, the typical sites for muscle biopsy are deltoid or biceps. We want to focus on the bicep muscle only and we will include only patients with brachial–cephalic AVF in the elbow or brachial–basilic AVF in the arm will be selected in order to have easily access to the biceps muscle.

The skin incision for closing brachial–cephalic or brachial–basilic AV fistula in the upper extremity is made over the area of the arteriovenous anastomosis: in the elbow for brachial–cephalic AVF or in the arm for brachial–basilic AVF.

After shaving and disinfection of the external part of the surgical site, local subcutaneous anaesthesia is achieved using 4 mL of lidocaine (2%) with special attention to ensure that no lidocaine is injected in the muscle. Thus, injection of lidocaine is done superficially and obliquely.

In case of voluminous fistula, a regional anesthesia via peripheral nerve block is preferred. In these cases, the anesthetic (a mix of lidocaine and ropivacaine) is injected by anesthesiologist near the brachial plexus to block sensations of pain from a specific area of the body. Nerve blocks usually last longer than local anesthesia.

A small cutaneous incision (about 4-5 cm) is made in the antecubital fossa, over the area of the arteriovenous anastomosis, following the medial border of the biceps muscle. The muscle is retracted slightly laterally in order to allow access to the thin aponeurotic sheath which contains the neuro-vascular bundle. Biceps brachii muscle is visualized and cut. Muscle fibres are carefully dissected in their longitudinal axis away from the tendon insertion, to obtain a sample of 300 mg. This is about the size of 2-3 grains of rice. Both ends are immediately clipped and hemostasis is controlled. The bundle is fixed on a cork support at its apparent resting length.

The skin incision is closed with 3.0 Nylon suture and pressure is applied to the incision site.

This procedure will be done once at 12 months for patients randomized to the exercise arm (after the exercise intervention is completed) and once at any time during the 12 month study duration for the control arm as long as the patient is at least one year post transplant.

Status of systemic inflammation

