Week 42	1 Warm Up Set: 8 – 12 reps. 1 Heavy Set: 8 – 12 reps. Slower Speed.	Moderate/Heavy	2 minutes
Week 43	3 Sets on each exercise of 6, 8, 12 repetitions. Lower weights each set. Medium speed.	Moderate	3 minutes
Week 44	1 set 90 seconds focused on resistance. Medium speed.	Lighter	2 minutes
Week 45	1 Warm Up Set: 8 – 12 reps. 1 Heavy Set: 8 – 12 reps. Slower Speed.	Moderate/Heavy	2 minutes
Week 46	3 Sets on each exercise of 6, 8, 12 repetitions. Lower weights each set. Medium speed.	Moderate	3 minutes
Week 47	1 set 90 seconds focused on resistance. Medium speed.	Lighter	2 minutes
Week 48	1 Warm Up Set: 8 – 12 reps. 1 Heavy Set: 8 – 12 reps. Slower Speed.	Moderate/Heavy	2 minutes
Week 49	3 Sets on each exercise of 6, 8, 12 repetitions. Lower weights each set. Medium speed.	Moderate	3 minutes
Week 50	1 set 90 seconds focused on resistance. Medium speed.	Lighter	2 minutes
Week 51	1 Warm Up Set 8 reps 1 Heavy Set 8 reps	Heavy	3 minutes
Week 52	Cardio Exercises. 10 exercises in a set. 2 Sets.	Moderate	3 minutes

GH Method: List of Strength/Resistance Exercises

MEN

WOMEN

Exercise

Exercise

Chest: Smith Bench Press/Incline	Glutes: Abductor
Glutes: Abductor	Biceps: Cable Easy Curl / Free Bar
Biceps: Cable Easy Curl/Free Bar	Quads: Leg Extension
Quads: Leg Extension	Chest: Smith Press
Calves: Calf Machine	Abs: Decline
Biceps: Preacher	Quads: Leg Press
Quads: Leg Press	Back: Pull Down Behind
Quads: Leg Extension	Hamstring: Machine
Abs: Decline	Shoulders: Dumbbell Press / Smith Press
Back: Pull Down Behind	Triceps: Push Down / Kick Back / Rope Pull down
Hamstring: Curl Machine	Back: Low Roll
Shoulders: Dumbbell Press / Smith Press	Abs: Sit-Ups
Back: Low Roll	Shoulders: Side Raise with Dumbbells
Hamstring: Good Morning with Dumbbell/ 1 Leg Hamstring Curl	Triceps: Close Grip
Shoulders: Side Rise with Dumbbells	Hamstring: Good Morning with Dumbbells/1 Leg Hamstring
Triceps: Push Down / Kick Back	Triceps: Push Down / Kick Back
Abs: Sit Ups	Abs: Sit Ups
Triceps: Close Grip	Triceps: Close Grip

5)Statistical analyses:

The efficacy of the methods will be determined by:

1. a significant difference in term of pre and post treatment perception of well being between the groups
- 2.a significant difference in the lean/fat body mass ratio between the groups
3. a significant difference in BMI between the groups
4. a significant difference between the inflammatory parameters between the groups
5. a significant difference between the metabolic parameters between the groups

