
The data will be entered into an Excel spreadsheet and stored on the UIMCC hospital server. The patient data, including age, sex, race, underlying kidney disease, length of hospital stay, rejection episode, comorbidities, and medications will be coded and patient names will not be included in the datasheet.

The de-identified collected data will be entered into a SAS database. Initial descriptive analysis will include calculating means, standard deviations, ranges and frequencies. T-tests for continuous variables and Chi Square or Fischer exact tests of association for

categorical variables will be used to compare results of the study between the two groups for the efficacy parameters listed above. A P value<0.05 will be considered significant.

6) Benefits/risks

The main risk of this research is loss of confidentiality of medical information. Consent will be obtained for all patients. Master patient code list will be kept in a separate file accessible only by the primary investigator. A member of the transplant team will be available to answer any questions or discuss any concerns that patients may have.

The patient may experience mild anxiety or discomfort in providing information about their health and well-being. The patient may also have a potential to feel anxiety when being video recorded (if applicable).

Risks associated with the exercise program

The likely risks and discomforts expected in this study are those that largely involve being engaged in an exercise program after a prolonged period of inactivity. Such risks include: strains, sprains, and muscle soreness. Serious physical injury is considered unlikely given the screening for inclusion and physician approval. We will attempt to reduce risks of injury and harm by promoting gradual increases in exercise across time throughout the 3 month period and having exercise be instructed and supervised by trained professional fitness personnel.

Risks associated with the blood draw:

The risks associated with a blood draw include: mild pain, bleeding or bruising at the site of the draw. In general, any bruising should completely disappear within several days. There are minimal risks of fainting or hypotension (low blood pressure) during or after the blood draw.

Risks associated with the Maximal Aerobic Capacity Test (VO2 Test) and the 6 minute walk test include:

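### PROMIS well-being: the first form is tied to enrolment, which may precede the transplant, so an early enrollee's pre-post change could contain the transplant as well as the programme

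*Combined protocol and SAP*

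**What the plan says.** All references are to the combined protocol and SAP.

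- **Timing of PROMIS** (Parameters to analyze in all patients): the Global Health form and the PROMIS 29 are each "administered to all patients at the time of enrollment, 6 months and at the end of the study (12 months"), in both arms.
- **Enrolment and start of treatment** (Methods, Setting): "Patients will start the intervention at least 2 months post-transplant; however they can be enrolled prior to transplant".
- **Efficacy parameter** (Statistical analyses, first in the list): "a significant difference in term of pre and post treatment perception of well being between the groups". Hypothesis 6 ties well-being to the PROMIS forms. No parameter is named as primary.
- **Test** (Statistical analyses): "T-tests for continuous variables", with no adjustment for when the patient was transplanted.
- **Clock for later visits**: Hypothesis 3 covers PROMIS and says "levels will be documented with an accelerometer and PROMIS questionnaires, 6 months and 12months to document the effect of intervention". Hypothesis 4, on macrophages, is more explicit: "at baseline, 6 months and 12 months after the initiation of the intervention".

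Other text points to a later first measurement. The grid at the end of the document puts questionnaires in its baseline column. The GH-only forms are also timed at enrolment, yet only a randomized patient can be a GH patient. GH Study Visits has written assessments returned at least a week before the first GH session.

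**The concern.** The change in well-being is meant to show what the programme does. For a patient enrolled before surgery, a form completed at enrolment does precede the programme, but it also precedes the transplant and at least 2 months of recovery. The Background describes transplantation as restoring kidney function and reversing a catabolic state, and PROMIS asks about physical function, fatigue and pain. A shift in scores across the transplant is therefore plausible, though the documents give no size for it.

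Two things are at stake. The change within an arm could not be read as the effect of GH, or of standard care. And a mix of early and late enrollees would widen the spread of change scores, which an unadjusted t-test does not absorb. Nothing in the plan asks for a repeat PROMIS after transplant and before the intervention.

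**Working it through.** **1. The plan's own figures.** The plan states 225 patients, 180 GH and 45 control, randomized 4:1. The split checks: 225 × 4/5 = 180 and 225/5 = 45. It gives no power, effect size or SD, so the sample size itself cannot be reproduced. The 80% power used below is a reference point for scale, not a claim of the plan.

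**2. What the change spans.** Suppose a patient enrols k months before transplant and the 12 months run from the start of the intervention. The interval from first to last PROMIS is then at least k + 2 + 12 months: 14, 17 and 20 for k = 0, 3 and 6. The clock is inferred, mainly from Hypothesis 3, because the PROMIS paragraphs name no start point other than enrolment. Counting from enrolment instead would not help. The transplant would still fall inside the interval, and at month 12 the patient would have had at most 12 − (k + 2) = 10 − k months of GH.

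**3. Model for the precision loss.** Let f be the share enrolled before transplant and T the transplant's shift in PROMIS, in SD units of the change score among patients with the same timing. Both are assumptions. T is taken as constant and equal in the two arms, and the t-test is assumed to be applied to the change.

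- Expected transplant component of the mean change in each arm: f × T. It is the same in both arms, so it cancels from the between-arm difference in expectation.
- Variance of the change: V = 1 + f(1 − f)T².
- Standard error factor: sqrt(1/45 + 1/180) = 0.1667.
- Difference detectable with 80% power, two-sided 5% (the plan does not state sidedness): (1.960 + 0.842) × 0.1667 = 0.467 SD. This is the value if the first PROMIS is taken after transplant.
- With the shift present, the detectable difference is 0.467 × sqrt(V). Power for 0.467 SD is Φ(2.802/sqrt(V) − 1.960).

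| f | T | V | Detectable difference (SD) | Power for 0.467 SD |
|---|---|---|---|---|
| 0 | any | 1 | 0.467 | 80.0% |
| 0.10 | 0.25 | 1.006 | 0.468 | 79.8% |
| 0.10 | 0.5 | 1.023 | 0.472 | 79.1% |
| 0.10 | 1.0 | 1.090 | 0.487 | 76.5% |
| 0.25 | 0.25 | 1.012 | 0.470 | 79.5% |
| 0.25 | 0.5 | 1.047 | 0.478 | 78.2% |
| 0.25 | 1.0 | 1.188 | 0.509 | 72.9% |
| 0.50 | 0.25 | 1.016 | 0.471 | 79.4% |
| 0.50 | 0.5 | 1.063 | 0.481 | 77.6% |
| 0.50 | 1.0 | 1.250 | 0.522 | 70.7% |

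Using the t distribution with 223 degrees of freedom, the starting value is 0.469 SD instead of 0.467 and the powers are the same to the decimals shown. The worst row is equivalent to analysing 225/1.25 = 180 of the 225 patients.

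**4. The same variance seen as chance imbalance.** At f = 0.25, the SD of the between-arm difference in early share is sqrt(0.25 × 0.75) × 0.1667 = 0.072. The 95% range is therefore about ±1.96 × 0.072 = ±14 percentage points. Multiplied by T = 0.25 to 1, that moves the estimated difference by up to 0.04 to 0.14 SD. This is where the extra variance comes from, not a further loss.

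**The case against.** The best reply is that enrolment, as this protocol uses the word, means entry into the programme. The eligibility list requires "Successful kidney transplantation (KTx) with primary graft function", and randomization is open only to patients who meet the criteria. A GH-only form timed at enrolment must then come after transplant. BMI is timed at enrolment in one place and at baseline in two others, as if the terms were interchangeable. The grid groups questionnaires with DEXA and Biodex, whose baseline Hypothesis 2 places before the intervention. The grid's consent row does not tie that column to an early date either, since it is ticked at all three visits. The PROMIS forms also feed the GH coaching process, whose written assessments are tied to the first session. On this reading the Setting sentence merely permits early consent.

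Much of this stands, and it is why the point is conditional. It does not settle the matter. Setting says outright that enrolment can precede transplant, and eligibility for randomization does not date a questionnaire tied to enrolment. The one-week rule is a minimum with no maximum, and controls have no GH session to anchor to. The grid does not define baseline.

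Two further objections also have force. Hypothesis 2 expects the transplant itself not to change activity, strength or muscle mass; that is a hypothesis about neighbouring outcomes, not about well-being, but it is a caution against assuming a large shift. And if only 12-month values were compared, the first PROMIS would not enter the test; the listed parameter, however, refers to both pre and post.

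A reader might infer that the comparison of GH with control is biased. The documents do not support that: the same timing rule applies to both randomized arms.

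**Conclusion.** The point holds in a conditional form. As written, the enrolment rule for PROMIS and the permission to enrol before transplant together allow the transplant and recovery to fall inside the well-being change of early enrollees. Other parts of the protocol suggest a later baseline, and the text does not choose between the two.

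If the literal rule is followed, within-arm change cannot be read as the programme effect, and a t-test on change scores loses some precision. The between-arm difference remains unbiased in expectation. A reader might also take the loss to be about nine power points; that needs half the patients enrolled early and a full 1 SD shift, and neither figure is in the documents. With a 0.25 SD shift the loss is under 1 point at every share considered, and with nobody enrolled early it is zero. The severity is minor.

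**What to change.** In the PROMIS paragraphs, replace the enrolment timing with: *at the baseline procedure visit, at least 2 months post-transplant and before the first GH session (or the matching date in controls), and 6 and 12 months after that date*. Make the same change to the BMI sentence under Body composition and strength, for consistency with the other places that already put BMI at baseline. Use any earlier enrolment value for description only. In the GH arm the forms can still be completed a week or more before the first session, so the existing rule on written assessments is kept.

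The cost is a wording change. Early enrollees who already completed the forms repeat two short questionnaires, 10 items plus 4 × 7 + 1 = 29 items. The baseline procedure visit already exists, so no visit is added.
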